11.5 Adverse Events

Anticipated AE and possible precautions and responses to these events include:

- 1) Discomfort caused by completion of survey questions.** Most questions and measures used in the study are standard for medical or psychological evaluations and therefore have minimal risk associated with them. These questions may address issues of family psychiatric history, parental relationships, significant depression/self-harm, and family substance abuse. Participants and parents are free not to answer any questions to which they object. Also, teens with ADHD may experience frustration when completing cognitive and neuropsychological tasks if the testing lasts longer than their attention span or if they are being asked to complete items that are challenging for them. Our evaluators have clinical expertise in evaluating teens with ADHD and if teens are exhibiting fatigue or frustration, families will be given the option of stopping the assessments and returning at another time to complete them.
- 2) Identification of high-risk substance use.** If a 16- or 17-year-old is excluded because of their score on the SSI-AOD indicating that they are at risk for substance abuse, we will follow these steps:
 1. A clinician will meet with the 16- or 17-year-old child and provide them with resources for substance use assessment and treatment in the community so that they may seek help. We will give the teen the opportunity to insert the information into their phone or have the information emailed to their private email in order that this remains private health information. The family will be informed that the research staff has determined that the teen does not meet our inclusion/exclusion criteria with no specifics about which criteria were not fulfilled.
 2. Further, the SSI-AOD will be checked to see if the 16- or 17-year-old responded affirmatively to critical items on the SSI-AOD reflecting that the teen's substance use may be putting him/her or others at risk for significant harm ("been injured after drinking or using", "been arrested or had other legal problems (such as driving while intoxicated)", or "When drinking or using drugs, are you more likely to do something you wouldn't normally do, such as break rules, break law, sell things that are important to you, or have unprotected sex with someone?"). If so, a clinician will meet with the 16- or 17-year-old to further interview the teen about these items and make a clinical determination if the child is at risk of significant harm to self or others. If so, the parents of the minor will be notified of the issue and the family will be given resources for substance use assessment and treatment in the community.
 3. The SSI-AOD substance use measure will also be collected at the 6-month assessment point. If the teen has a score of 4 or more indicating "Moderate to high substance use and possible need for further assessment", a clinician will meet with

the 16- or 17-year-old child and provide them with resources for substance use assessment and treatment in the community so that they may seek help. We will give the teen the opportunity to insert the information into their phone or have the information emailed to their private email in order that this remains private health information.

At the 12-month timepoint, we will again collect the SSI-AOD but since there is no in-clinic visit, the SSI-AOD will be collected via REDCap survey. The REDCap survey will be programmed so that if the teen has a score of 4 or more indicating “Moderate to high substance use and possible need for further assessment”, the teen will be presented with text indicating that they have scored in the problematic range and providing them with resources for substance use assessment and treatment in the community so that they may seek help.

- 3) Simulator sickness including nausea and headache.** The simulator tasks may elicit a mild stress response. When participants are instructed to engage in a secondary task, drivers may experience feelings of annoyance, and participants may experience minor muscle fatigue due to the length of driving time. There is a slight risk that participants may experience nausea from the simulator. In order to limit motion sickness from the simulator, there will be a fan providing air flow in the simulator room, and all participants will be provided with a SeaBand which is worn around the subject’s wrist and uses acupressure to reduce nausea and motion sickness. Also, we have limited training driving sessions to 5-minute lengths with breaks in between in order to reduce risks of motion sickness.
- 4) Negative impact of medication wash-out on teen driving.** Teen participants who take medication for ADHD will be asked to refrain from taking their medication on the days of simulator driving assessments. Parents will be informed of the risks associated with this (i.e., driving safety, school performance, job performance, etc.). In order to limit the risk associated with a medication washout, both the teen and parent will be advised verbally and in writing that the teen is not to drive to the study appointments and must be driven by the parent. In addition, the study coordinator will make a reminder phone call prior to the driving assessment. During this call, the coordinator will remind parents and teens that parents are to drive un-medicated teens to their appointment. Participants are free to resume medication immediately following the study visits.
- 5) Breach of confidentiality.** The potential for a breach in confidentiality always exists, specifically with the written research data and study databases. Study procedures have been designed to protect the privacy and confidentiality of the research participants. Throughout the study, all data, including that collected during the screening and recruitment phase will only be identified by a unique identification number and participant code using letters and numbers to protect against invasion of privacy. The data will be blinded correspondingly in all data analyses. Only authorized staff will have access to participant information. All study information containing identifying information will be stored separately from the study data and will be stored in a locked filing cabinet. Binders with identifying information (e.g., consent forms) will be maintained separately from the evaluation, assessment and outcome data. All data will be entered into an electronic database for storage and analysis. Information will be entered into computers by participant number, not name, in order to protect the identity of the participants and their parents. No personal identifying information will be used in conjunction with the electronic form of the generated data. The database will be accessible by password only by project personnel. Research papers will be based on analyses of group data with no identifying information about any participant used in these reports. For students who complete the Qualtrics Survey via the SONA system, all

electronic data will be kept on password-protected computers and protected by a firewall. Only the researchers will have access to the data.

- 6) **Incriminating DriveCam recordings.** Driving will be assessed using an in-car video recorder (DriveCam) which will be installed in the identified “teen car.” There is a risk that the video recordings could capture video that could be used to incriminate the driver of the car and/or another driver in terms of driving behavior or other illegal behavior. We have obtained a federal Certificate of Confidentiality in order to protect video recorded driving information collected with DriveCam monitoring. All teen drivers will be consented in order to be protected by the Certificate of Confidentiality. Moreover, parents will be told during consent that we will not be sharing the recorded video footage with anyone. If the teen or parent(s) later request to view the footage (e.g., following a driving incident or MVC), the study staff will review the footage and provide the family with a summary of incident-related information visible in the recorded footage (e.g., number of passengers present, driver engagement in another task, etc.). If the family further presses to view the driving footage, the PI will contact the family to discuss Certificate of Confidentiality stipulations prior to releasing any footage information. Additionally, families will be explicitly told that video recordings collected using an in-car video recorder (DriveCam) will be collected on anyone driving the identified “teen car”. Moreover, an information card will be provided each family to keep in the car so that anyone who drives the car or is a passenger in the car is aware that they will be video recorded. However, research staff will immediately destroy all video in which the teen participant is not the driver. Further, families will be informed that all video recordings will be destroyed immediately after the study period.
- 7) **MVC involvement.** Please see 8.5 Interim Analyses for information regarding safety monitoring.

Unanticipated AE: An adverse event whose nature, severity or frequency is inconsistent with the underlying disease, disorder, or condition of the subject, and is not identified in the informed consent document.

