- i. Successful calibration on eye tracker: All participants must receive $\geq 80\%$ of data captured during Georgia Tech Simulator Sickness Survey 2-minute pre-test drive.

Exclusion Criteria:

Participants will be excluded from the study if they meet any of the following criteria:

- a. Understanding level: The participant and parent cannot understand or follow instructions given in the study as determined by study staff discretion at primary visit.
- b. On neuroleptic medications or medications for ADHD that cannot be washed out on assessment days.
- c. Risk for alcohol or drug abuse. **Rationale:** Teens engaging in significant abuse behaviors as assessed using the Simple Screening Instrument for Alcohol and Other Drugs (SSI-AOD) (Winters & Zenilman, 1994) likely require more intensive and other interventions. Participants with a score of 4 or higher on the SSI-AOD will be excluded from the study.

- d. Cannot see the secondary task stimuli without the use of glasses (contacts acceptable).
Rationale: The eye tracking equipment that will be used during driving simulation to measure eye glances cannot be used if the participant is wearing glasses
- j. Risk for motion sickness in driving simulator: During phone screening, participants will be asked a series of questions on the Simulator Sickness Questionnaire that are designed to measure propensity for motion sickness. If the participant indicates that they “Nearly Always” get motion sickness in at least 4 of the situations, they will be excluded from the study. In addition, at the baseline visit, each participant will complete the Georgia Tech Simulator Sickness Screening Survey (GTSSSS) (Gable & Walker, 2013). After they complete the survey, they will complete a 2-minute practice drive in the driving simulator. After the practice drive, they will complete the GTSSSS a second time. If any single rating on the post-drive survey is greater than or equal to 5 more than pre-drive survey, or if any three of the ratings on the post-drive survey are above a 3 as compared to the pre-drive survey, the participant will be excluded.

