- 4) Vanderbilt ADHD Parent Rating Scales (VAPRS) (Wolraich, Lambert, Doffing, Bickman, Simmons, & Worley, 2003): This DSM-based checklist allows parents to rate the teen on each of the 18 ADHD core symptoms. Parents also rate the teen on a variety of domains of functional impairment. Internal consistency and reliability are excellent (Wolraich et al., 2003).

- 5) Georgia Tech Simulator Sickness Screening Survey (GTSSSS) (Gable & Walker, 2013): Participants complete the GTSSSS prior to driving in the simulator. The participant drives through the scenario as they would in a regular vehicle, observing all traffic laws. Following completion of the driving scenario participants return to the post-drive survey.
- 6) Simple Screening Instrument for Alcohol and Other Drugs (SSI-AOD) is a 16-item screening instrument including yes/no questions about the respondent's experience with alcohol and other drugs in the past 6 months (Winters & Zenilman, 1994). It covers drug use, preoccupation and loss of control, adverse consequences, problem recognition, and tolerance and withdrawal. This questionnaire will be administered during the in-person visits at Baseline and 6-months. In addition, this questionnaire will be sent as a REDCap survey for teens to complete at the 12-month time point.
- 7) Kaufman Brief Intelligence Test-2 (K-BIT); Kaufman & Kaufman, 2004): The K-BIT is a culturally-sensitive standardized assessment that estimates verbal and non-verbal and overall intelligence. This test has good reliability and validity and will be administered to assess each child's intelligence and rule out possible intellectual disability.
- 8) Driving History Questionnaire (Laboratory Developed): The Driving History Questionnaire is a brief laboratory developed questionnaire assessing relevant driving history such as date of licensure. This questionnaire will be administered during the in-person visits at Baseline and 6-months. In addition, this questionnaire will be sent as a REDCap survey for teens to complete at the 12-month time point.

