6.4 Study Assessments

Frequency and Timing of Relevant Assessments:

	Baseline/Randomization	1-month follow-up assessment	6-month follow-up assessment	12-month follow-up
Diagnostic and Clinical Assessment	X			
Driving Simulation Assessment		X (2 runs)	X (2 runs)	
DriveCam Recording	X (Installation)	← CONTINUOUS →		
Driving Records		← CONTINUOUS →		
Adverse event monitoring		← CONTINUOUS →		

Analysis Time Windows:

Visit (target day)	Lower bound (days)	Upper bound (days)
Baseline/Diagnostic and Clinical Assessment (-7)	-14	-7
Randomization/Training 1 (0)	N/A	N/A
Training 2 (7)	4	10
Training 3 (14)	11	17
Training 4 (21)	18	24
Training 5 (28)	25	31
Month 1 (30 post-training 5)	30	45
Month 6 (180 post-training 5)	180	195
Month 12 (360 post-training 5)	Not in person	Not in person

Study Variables:

Primary Endpoint Variables Collected During Secondary Task (ST) Performance Portion of Driving Simulation:

1) Extended eye glances: This variable will be a frequency count of the number of ≥ 2 secs glances. Extended eye glances of interest are those occurring during the ST portions of the drive. The range for this variable could range from 0 to 100.

2) Standard Deviation of Lane Position (SLDP): Standard deviation of lane position will be calculated during the ST portions of the drive. An average of 0 indicates that an individual maintained consistent lane position. The range for this variable is from 0 to 3

Secondary Endpoint Variables Collected using DriveCam:

1) Extended eye glances: As has been done in previous research, the number of ≥ 2 sec eye glances away from the roadway occurring between -5 secs before to 1 sec after the event causing a .6 g-force will be calculated (Dingus, Klauer, Neale et al., 2006). For each event video, we will code the onset and offset of glances away from the roadway. Based on the onset and offset times, we will calculate whether the video clip contains a continuous eye glance away from the roadway that lasts for 2-seconds or longer between -5 secs before to 1 sec after the event. It is possible that some participants will not contribute any data at all to this outcome variable due to not experiencing any .6 g-force events during the 12-month observation. The lower end of the range for this variable for participants who do experience at least 1 .6 g-force event during the observation period is 0. There is no upper limit to this variable.

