9.6 Derived variables

- **Participant Age:** (moderator for supplemental analyses). Age will be measured in years (using decimals; range 16.00-19.99) and will be calculated by subtracting the participant’s date of baseline visit from their date of birth
- **Stimulant medication status:** dichotomized based on whether the teen reported taking ADHD medication at any point during the 12-months of naturalistic driving.

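### The 6-month response to a positive substance-use screen names only 16- and 17-year-olds, so participants aged 18 or older at that visit have no stated screen-specific response until the 12-month survey

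*Combined protocol and SAP*

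**What the plan says.** SAP 6.2 screens substance use at entry with the SSI-AOD: "Participants with a score of 4 or higher on the SSI-AOD will be excluded from the study". The same section says of the instrument: "This questionnaire will be administered during the in-person visits at Baseline and 6-months". A REDCap survey repeats it at 12 months. Section 6.2 admits ages 16 to 19 and expects 18-year-olds, who sign their own consent. Section 9.6 puts it this way: "Age will be measured in years (using decimals; range 16.00-19.99".

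SAP 11.5, item 2, sets out the responses to a positive screen:

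- **Baseline (steps 1 and 2).** The item opens: "If a 16- or 17-year-old is excluded because of their score on the SSI-AOD". A clinician gives resources privately. If critical items are endorsed and a risk of significant harm is found, the parents of the minor are told.
- **6 months (step 3).** The screen "will also be collected at the 6-month assessment point. If the teen has a score of 4 or more", which triggers a clinician meeting with "the 16- or 17-year-old child and provide them with resources for substance use assessment and treatment in the community". The teen may then save that information to a phone or private email.
- **12 months.** For a score of 4 or more on the survey, "the teen will be presented with text indicating that they have scored in the problematic range", together with resources. No age is named.

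**The concern.** Within one sentence of step 3, the trigger and the action cover different groups. The trigger is any teen with a score of 4 or more. The action is for 16- and 17-year-olds. The sentence about saving the information depends on the clinician meeting, so it does not widen the action.

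Followed as written, an 18- or 19-year-old gets less than a 17-year-old with the same score at the same in-person visit. These are teens selected for at least 3 hours a week of unsupervised driving (SAP 6.2), and the SAP itself treats the score as a possible need for further assessment. What is at stake is the consistency of a safety procedure, not any inference about the intervention.

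**Working it through.** The plan states no figure to reproduce. The check has two parts: whether another provision fills the gap, and which ages fall into it.

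**Other provisions that might apply at 6 months to a participant aged 18 or older**

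| Provision | Whom and when it covers | Fills the gap? |
|---|---|---|
| SAP 11.5 item 2, steps 1 and 2 | 16- and 17-year-olds, baseline screen | No |
| SAP 11.5 item 2, 12-month step | Any teen scoring 4 or more on the survey | Later only; needs a new positive score; text, no clinician |
| SAP 6.1, Eligibility Assessment | Serious psychopathology found at the evaluation, and people who do not meet study criteria | No; eligibility stage |
| SAP 9.9 | SSI-AOD score of 4 or more as a baseline exclusion | No; gives no response |
| Protocol 6.b, Adverse events | Follow-up and treatment for any adverse event | In general terms; does not mention the screen |
| Protocol 6.e | Adverse-event enquiry at each assessment visit; the principal investigator is responsible for safety | In general terms; does not mention the screen |

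No provision states a response to the 6-month screen for this age group. The last two rows apply at all ages, but only if a positive screen is handled as an adverse event. SAP 11.5 supports that by listing high-risk substance use among anticipated events.

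**Ages affected**

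Inputs:

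- SAP 6.4 windows: baseline 14 to 7 days before training 1 (day 0); training 5 on days 25 to 31; the 6-month visit, listed as "Month 6 (180 post-training 5", 180 to 195 days after training 5; month 12 at a target of 360 days, not in person.
- SAP 5.2: if training is incomplete, the post-training period starts at the last completed session.
- SAP 9.6: baseline age from 16.00 to just under 20, a span of 4 years.

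Days from baseline to the 6-month visit = (baseline to training 1) + (training 1 to last session) + (last session to visit):

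- Shortest, only training 1 completed: 7 + 0 + 180 = 187.
- Nominal, all five sessions on target: 7 + 28 + 180 = 215.
- Longest, all five sessions at the upper windows: 14 + 31 + 195 = 240.

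Baseline age at which a teen is 18 by that visit = 18 − days/365.25. Share of the eligible span = (20 − that age)/4:

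| Days | Threshold age | Share of age span |
|---|---|---|
| 187 | 18 − 0.51 = 17.49 | 2.51/4 = 63% |
| 215 | 18 − 0.59 = 17.41 | 2.59/4 = 65% |
| 240 | 18 − 0.66 = 17.34 | 2.66/4 = 66% |

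If the phrase means age at baseline instead, the share is (20 − 18)/4 = 50%.

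Time to the next stated response: 360 − 195 = 165 to 360 − 180 = 180 days, taking month 12 at its target because it has no window.

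**The case against.** The best answer is that this is an editorial slip that no sensible clinician would follow. Section 11.5 introduces its items as possible precautions and responses, so the list does not claim to be complete. Step 3 sits under an item that opens with teens excluded at baseline, who have no 6-month visit, so its wording was plainly brought in from there. The trigger, the follow-on sentence and the 12-month step all speak of the teen, which suggests that every age was meant. Protocol 6.b and 6.e place general duties on the investigators at every age. The change log (SAP 14.8, 10/16/2017) also mentions a protocol section on risks and precautions that is not in the supplied text, so working safety wording may exist elsewhere.

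Most of this stands and lowers the seriousness. It does not supply the missing action, because step 3 is not silent on age: it states a limit. The limit has no evident purpose there. Parental notification, where being a minor matters, belongs to step 2; step 3 only hands over resources privately.

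Two stronger readings are tempting. A reader might infer that older participants had no safety cover at all, or that someone went without help. The general duties rule out the first, and nothing in the documents shows the second. A reader might also take 63% to 66% as the share of participants affected. The documents give neither an age distribution nor a rate of new positive screens, so that does not follow.

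**Conclusion.** The mismatch is real and minor. As written, enrolled participants aged 18 or older at the 6-month visit have no stated screen-specific response until the 12-month on-screen text, and then only if they score 4 or more again. No step gives them a clinician meeting. General adverse-event and safety duties still cover them.

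The age thresholds rest on the SAP 6.4 windows and the last-session rule in 5.2. The 240-day figure is a nominal upper value, because the log in SAP 14.8 (10/10/2018) relaxed the weekly spacing of sessions. How many people are affected is unknown and may be zero, since scores of 4 or more are excluded at baseline. No endpoint, alpha level, sample size or analysis changes.

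**What to change.** In SAP 11.5, item 2, step 3, replace the words that name a 16- or 17-year-old with 'the teen', so that the clinician meeting and the resources apply at every enrolled age. This changes one phrase, with IRB review. It adds no visit, because the 6-month screen is already given in person.

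The log entries in SAP 14.7 from 06/23/2022 and 08/15/2022 respond to journal review, so the 6-month visits are probably complete and the wording change would then mainly correct the record. In that case an optional look-back could check stored 6-month scores, for at most 152 randomized participants, to see how anyone aged 18 or older with a score of 4 or more was handled. The check itself is small. Any re-contact to offer resources would need IRB approval and careful privacy handling, and that is the larger part of the cost.
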